The primary official permission will be obtained from the research ethics committee of faculty of nursing, Cairo University to approve the tools and the study. Also, the investigator will explain to the women the purpose and nature of the study and its importance. In addition, informed written consents will be obtained from women who were willing to participate in the study after ensuring that their participation is voluntary and the trial posed no risk or hazards on them. As well, each woman will be assured that she has the right to withdraw of the trial at any time without any effect on her care. Then, confidentiality will be assured through coding of data by the investigator and keeping the data in a secret place.

Validity and reliability

Un standardized tools were submitted to 3 experts in the field of maternity nursing to test content validity, clarity of sentences and an appropriateness of content. Modifications were carried out according to the expert judgment.

Procedure

First, the primary official permission will be obtained from the research ethics committee of faculty of nursing, Cairo University to approve the tools and the study. An official permission will be granted from the hospital administrative personnel in the recommended setting to collect the data. Then, data collection will be carried out through five steps in each group: Recruitment & randomization; interviewing; initial assessment; intervention; follow up and monitoring.

Recruitment and Randomization of sample: Women who will meet the eligibility criteria will be recruited from a written list done by the investigator every day. Those plotted in the odd number will be selected until completion of the sample. Random assignment of the subjects into two groups will be done through an opaque sealed envelope reflecting the type of each group, and then the eligible women will be asked to choose an envelope to

determine their groups.

Interviewing: During interview the aim of study will be explained to the women in both groups (study & control group) to gain their acceptance to participate in the study then data related to socio-demographic status and obstetric history will be collected from both groups

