Initial Assessment: Initial assessment for women in both groups (study & control group) will be carried out in relation to body mass index (BMI), type of perineal trauma after delivery (episiotomy, or tears), degree of perineal tear (1st or 2nd degree tear), and assessment of perineal trauma condition will be done using standardized REEDA scale . Also, women will be asked to indicate the degree of perineal pain using Visual Analogue Scale for pain intensity (VAS).This assessment will take 15 minutes for each woman.

Intervention:

Intervention for the study group: For the study group the intervention will be according to a designed protocol of care that entails; 1) Application of ice gel pad on perineal trauma for the first 24 hours post partum; 2) Performance of pelvic floor exercises (Kegel exercises) from six hours till one week postpartum; 3) Application of warm compresses after 48 hours and through the first week postpartum. The investigator will perform demonstration and then redemonstration by the women on each intervention will be done. A designed booklet (developed previously) that explains each intervention will be given to each woman.

Immediately after delivery (within 30 minutes to one hour after delivery), an ice gel pad will be applied to perineal trauma. It will be available in an individual package(every woman will alternate between two ice gel pads); each gel pad will have fixed standardized diameter (an approximately 5 cm width, 23 cm length, and 1.5 cm thickness) and approved by Egyptian ministry of health. It will be kept in the freezer for 45–60 minutes and

will be removed when frozen. Then, it will be wrapped in a sterile pad and applied to cover the perineum and anal region. The pad will be compatible with the anatomical structure of the perineum.

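### As the Procedure is written, women draw their group envelope before their acceptance is sought and before baseline VAS and REEDA are recorded, so refusals and baseline scores can depend on allocation

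*Combined protocol and SAP*

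**What the plan says.** The Procedure section says that data collection runs "through five steps in each group: Recruitment & randomization; interviewing; initial assessment; intervention; follow up and monitoring". The steps are then described in that order.

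- **Recruitment and Randomization of sample.** "Women who will meet the eligibility criteria will be recruited from a written list done by the investigator every day". From that list, "Those plotted in the odd number will be selected until completion of the sample". Then "the eligible women will be asked to choose an envelope", and the envelope fixes the group. The women drawing are described as eligible, not as consented.
- **Interviewing.** The aim "will be explained to the women in both groups (study & control group) to gain their acceptance to participate in the study". Demographic and obstetric data are collected after that.
- **Initial Assessment.** BMI, trauma type and tear degree, REEDA and self-reported VAS pain are recorded, again for women described by group. This takes 15 minutes.
- **Intervention.** Treatment by group starts here.

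The only other statement on consent is under Ethical consideration: "informed written consents will be obtained from women who were willing to participate in the study". It does not say whether this comes before or after the draw. The Statistical plan compares pain and healing scores with an independent-samples t test, two-sided at 0.05. It defines no analysis set and gives no rule for a woman who declines after drawing.

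**The concern.** Consent and baseline measurement normally come before allocation, so that neither can be affected by it. Here the written order is the reverse, with two consequences of unequal weight.

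**Refusal after the draw.** If a woman learns her group and is then asked to take part, her answer can depend on the group. The arms differ visibly in burden. The study arm involves repeated ice-pad applications over the first day, 25 pelvic floor contractions daily, a vaginal examination by the investigator during the exercises, and warm compresses three times a day. The control arm has routine care only. The women analysed may then not be the women randomised, and this affects the primary comparison directly. Selection continues until the sample is complete, and nothing says whether a decliner is counted, dropped or replaced. If decliners were replaced until each arm held 50, the final counts would hide the loss.

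**Baseline scores after the draw.** VAS is self-reported and REEDA is rated by an observer. Both can be coloured by knowledge of the group. They do not enter the unadjusted t test, so the primary test is not affected by this route. What suffers is the baseline comparison of VAS and REEDA. Age, parity and trauma type are facts that allocation is unlikely to alter.

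**Working it through.** **Order of events.** The plan has no figure of its own to reproduce here, so the main check is to set the text side by side.

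| Step as listed | What happens | Is the group already fixed? |
|---|---|---|
| 1 Recruitment and randomization | Eligible women choose an envelope | Fixed in this step |
| 2 Interviewing | Aim explained, acceptance sought | Yes |
| 3 Initial assessment | Baseline REEDA and VAS | Yes |
| 4 Intervention | Treatment by group | Yes |
| 5 Follow up | Telephone calls, day 7 visit | Yes |

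The step list, the envelope sentence and the repeated group labels agree. Opaque sealed envelopes conceal the assignment only until the draw. No sentence places consent or baseline before the draw.

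**Possible size.** From the documents: 50 women per arm and a two-sided 5% t test. Assumed, because the documents give no values:

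- one arm only loses a share q of its women after the draw: 5%, 10% or 20%;
- those lost are all from one extreme of a normally distributed trait;
- the trait's correlation ρ with the outcome is 0.3 to 0.5;
- there is no true treatment effect.

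The shift in the mean of that arm, in SD units, is

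shift = ρ × φ(z₁₋q) / (1 − q),

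where φ is the standard normal density. The factor multiplying ρ is:

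- q = 5%: 0.1031 / 0.95 = 0.109
- q = 10%: 0.1755 / 0.90 = 0.195
- q = 20%: 0.2800 / 0.80 = 0.350

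The rejection rate comes from the noncentral t distribution with noncentrality shift / √(1/50 + 1/n₂) and 50 + n₂ − 2 degrees of freedom. Without replacement n₂ = 50(1 − q), that is 47.5, 45 or 40. With replacement n₂ = 50.

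| q | ρ | Shift (SD) | Rejection rate, not replaced | Rejection rate, replaced to 50 |
|---|---|---|---|---|
| 5% | 0.3 | 0.033 | 5.3% | 5.3% |
| 5% | 0.5 | 0.054 | 5.8% | 5.8% |
| 10% | 0.3 | 0.058 | 5.9% | 6.0% |
| 10% | 0.5 | 0.097 | 7.6% | 7.7% |
| 20% | 0.3 | 0.105 | 7.8% | 8.1% |
| 20% | 0.5 | 0.175 | 12.9% | 13.9% |

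With ρ = 1, meaning that women sort themselves perfectly on the outcome, the shifts are 0.109, 0.195 and 0.350 SD. That is an unrealistic ceiling.

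**Cross-check with a simpler model.** If a share r of one arm refuses and refusers differ from stayers by g SD, the shift is r × g. With r = 10% and g = 1 it is 0.10 SD, and the rejection rate at 50 per arm is 7.9%. This agrees with the row for q = 10% and ρ = 0.5 (0.097 SD, 7.7% replaced).

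The stated effect size of 80% is not used in any of this.

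**The case against.** The strongest reply is that this is loose drafting. Recruitment and randomization form one combined heading, and the phrase about women in both groups may mean only that both arms get the same interview and baseline. The ethics paragraph precedes the Procedure and is compatible with consent first. A woman could hardly be asked to choose a group envelope without being told something about the study. This stands to a degree: practice may have been sound, and the text does not prove that any woman knew her group when she accepted. It does not remove the point. The order is stated, three separate pieces of text agree on it, and a reader who follows it exactly would randomise first.

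The size is also open to challenge. Every input is assumed, only one arm loses women, and all losses come from one extreme. Refusal would in practice be noisier and could occur in both arms, which would usually give smaller shifts. Even on these assumptions, 5% loss gives no more than 5.8%, and only the 20% loss with replacement takes the rate above 8% at both correlations. This is accepted; it argues for a moderate weight.

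Two narrower objections also stand. Replacement by arm is a possibility that the text leaves open, not a stated plan. And a woman who refuses at the acceptance step leaves no outcome data, so an analysis rule cannot recover her; for her, reporting is what matters.

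**Conclusion.** The concern holds for the Procedure as written. Allocation precedes both acceptance and the baseline VAS and REEDA, and nothing elsewhere in the documents corrects that order. Refusal after the draw can bias the primary comparison. The later baseline weakens only the comparability check on VAS and REEDA.

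The amount of bias cannot be determined from the documents. It is zero if refusal is unrelated to outcome. Under the assumed one-sided losses of 5% to 20% and correlations of 0.3 to 0.5, it is 0.03 to 0.18 SD, with a true two-sided error rate of 5.3% to 12.9%, or up to 13.9% with replacement. Small refusal rates would do little harm. This should be fixed, but it does not by itself invalidate the trial. Confidence is medium, because actual practice may have differed from the text.

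**What to change.** Reorder the existing steps:

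1. Confirm eligibility, including BMI and trauma type and degree.
2. Explain the study and obtain written consent.
3. Collect interview data, baseline VAS and baseline REEDA.
4. Draw the envelope.
5. Start the intervention.

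Add to the Statistical plan that every woman who drew an envelope is analysed in her allocated group as far as data and consent allow. Add that no woman declining after the draw is replaced without this being reported, and that refusals and exclusions after the draw are given by arm.

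The cost is wording only. No visit, staff or measurement is added. Acceptance and the 15-minute baseline already come before the intervention step, so the total time before the first ice pad does not change. The constraint is that consent and baseline must be finished before the draw, within the early postpartum window the protocol already sets.

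The Statistical plan is written in the past tense, so enrolment may be complete. In that case the order cannot be changed. The report should then state the order actually used and give post-draw losses by arm.

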The investigator will provide a clear and concise information through oral and written instructions about the following; 1) The ice gel pad's purpose, benefits, anticipated effects and how to apply it, 2) Apply the ice gel pad on perineum after birth within 30 minutes to an hour, 3) Instruct the women to apply the ice gel pad for about 20 minutes every two hours during the first 24 hours postpartum only, 4) The perineal pad should be changed regularly every two hours to prevent infection. This session will take 30-40 minutes for each woman. Then, six hours after the ice gel pad application, assessment of experienced perineal pain will be done using Visual Analogue Scale for pain intensity (VAS) and assessment of perineal trauma condition will be done using standardized REEDA scale.

Also, six hours after birth women will receive instructions to practice pelvic floor exercises (Kegel exercises) and will be asked to perform these exercises from 6 hours postpartum and continue at home till one week. Before applying the technique, the investigator will teach the women how to recognize the accurate muscle, whereby she imagines holding passing gases or trying to stop the flow of urine midstream at the same time. The women will be taught to insert a clean finger into the vagina before practicing the exercises and if the women feeling pressure around her finger, she is on the right track, the mother also will be instructed to place a hand on her belly during the exercises to make sure that it is kept relaxed.

The investigator will perform vaginal examination while the woman is doing the pelvic floor exercises (Kegel exercises) to ensure correct use of muscles. The investigator

will instruct the women to continue contracting the muscles for about 5 seconds and then to loosen them for 5 seconds and repeat it for five times each set, perform at least five sets per day (total 25 contractions each day will be performed). The mother will be instructed to perform these five sets of exercises at the rest period between other intervention (application of cold compresses for the first 24 hours and application of warm compresses after 48 hours) with at least two hours rest between each set.

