In addition, women will be instructed to apply warm compresses on perineal trauma 48 hours postpartum +at home. This will be done by using a clean pad soaked in warm water and squeezed to remove excess water then placed gently on the perineum, the warm compresses will be applied for 15 minutes three times per day (every 8 hours), and water in the bowl will be replaced with every application. Women will be asked to apply warm compresses on perineal trauma from 48 hours postpartum till one week. Also, before discharge each woman will have an explanation of Visual Analogue Scale for pain intensity (VAS) and they will be trained to indicate level of perineal pain using it. This session will take 30-40 minutes for each woman.

Intervention for the control group: The control group will receive the routine hospital care only. Then, six hours after delivery, assessment of experienced perineal pain will be done using Visual Analogue Scale for pain intensity (VAS) and assessment of perineal trauma condition will be done using standardized REEDA scale.

Follow up and monitoring: Follow up will be done by telephone calls and by postpartum visit at the seventh day:

For intervention group follow up by telephone call will be done at 24 hours to assess the following; degree of perineal pain using Visual Analogue Scale for pain intensity (VAS),

the women compliance with ice gel pad application for the first 24 hours, the women's need for additional analgesia and assess women's postpartum difficulty with performing functional activities as turning/ rolling in bed, getting out of bed, sitting, walking, defecation and urination using Visual Analogue Scale(VAS) for rating functional activities.

Also, telephone follow up will done at third and fifth day postpartum to assess degree of perineal pain using Visual Analogue Scale for pain intensity (VAS) and assess women's postpartum difficulty with performing functional activities as turning/ rolling in bed, getting out of bed, sitting, walking, defecation and urination using Visual Analogue Scale(VAS) for rating functional activities. The investigator will also assess mother compliance with the performance of pelvic floor exercises (Kegel exercises) and application of perineal warm compresses using postpartum follow up sheet.

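### Only the study arm is told what the ice pad should do for it, and VAS training and call order also differ by arm, so self-rated pain and function can drift toward the study arm for avoidable reasons

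*Combined protocol and SAP*

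**What the plan says.** The Outcome measures section makes perineal pain severity a primary outcome and difficulty with functional activities a secondary one. Under Tools for Data collection, the woman herself rates both on 10 cm visual analogue scales.

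Under Procedure, allocation is visible: "Random assignment of the subjects into two groups will be done through an opaque sealed envelope reflecting the type of each group", and the woman picks the envelope. No text describes blinding of women, callers or assessors. Before any care starts, the arms hear the same thing: "During interview the aim of study will be explained to the women in both groups".

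After that they diverge. For the study group, "The investigator will provide a clear and concise information through oral and written instructions", and the first listed item is "The ice gel pad's purpose, benefits, anticipated effects and how to apply it". In addition, "The investigator will perform demonstration and then redemonstration by the women on each intervention will be done", and "A designed booklet (developed previously) that explains each intervention will be given to each woman". The pad session closes with "This session will take 30-40 minutes for each woman", and the same sentence closes the later paragraph on warm compresses and VAS training. That training, given before discharge, is described only in the study-group section. For the other arm, "The control group will receive the routine hospital care only".

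Under Follow up and monitoring, the study arm's 24-hour call lists pain, then pad compliance, then analgesia need, then the functional ratings. The control arm's call lists pain, analgesia need and function. The Statistical plan compares pain scores by an independent-samples t test at a two-sided 0.05 level and compares functional difficulty by chi-square.

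**The concern.** Women using ice, exercises and compresses cannot be blinded, and the plan is not at fault for that. The concern is with differences between the arms that the treatment does not require. One arm is told what improvement to expect and is then asked to rate whether it improved. The same arm is the only one for which training on the rating scale is described. At 24 hours it may also be asked about its treatment just before rating function.

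Each of these can move a subjective score without any change in the perineum, most plausibly toward the study arm. The planned tests compare the ratings as given and cannot separate such a shift from an effect of the therapies. The plan hopes its protocol will serve as guidance for practice, so a pain difference that mixes the two could be credited entirely to ice, exercises and compresses.

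**Working it through.** **Step 1. Set the arms side by side (Procedure; Follow up and monitoring).**

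| Item | Study arm | Control arm |
|---|---|---|
| Study aim explained | yes | yes |
| Expected benefits of the pad stated | yes, in one of four instruction items of the pad session | not described |
| Demonstration, return demonstration, booklet | yes | not described |
| VAS training before discharge | described | not described |
| Order at the 24 h call | pain, pad compliance, analgesia, function | pain, analgesia, function |
| Order at day 3 and 5 calls | pain, function, then compliance | pain, function |

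**Step 2. Find which ratings are exposed.**
- Pain VAS after the start of treatment: 6 h, 24 h, days 3, 5 and 7, in both arms.
- Functional VAS: 24 h and days 3 and 5 only. None is scheduled at 6 h or day 7.
- The 6 h pain rating comes six hours after the pad is applied in the study arm, so the benefit message can precede every pain rating after baseline.
- Call order: pain already comes first at every call. The only rating listed after a compliance question is function at 24 h in the study arm.

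**Step 3. See how far a shift could carry the test.** The plan gives no expectation effect and no SD for the VAS, so there is no plan figure to reproduce. This step is a sensitivity range.

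Inputs: n = 50 per arm (Sample section); two-sided alpha 0.05 and t test (Statistical plan); true treatment effect zero (assumed); total expectation shift d in SD units (assumed).

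- Degrees of freedom: 2 × 50 − 2 = 98; critical value t = 1.984.
- Noncentrality: d × √(n/2) = d × √25 = 5d.
- Rejection probability: P(T > 1.984) + P(T < −1.984), with T noncentral t on 98 df.

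| Assumed shift d | Noncentrality 5d | P(two-sided p < 0.05) |
|---|---|---|
| 0 | 0 | 5.0% |
| 0.1 | 0.5 | 7.9% |
| 0.2 | 1.0 | 16.8% |
| 0.3 | 1.5 | 31.8% |
| 0.4 | 2.0 | 50.8% |

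From 0.2 SD upward, nearly all of these rejections favour the study arm (16.6 of the 16.8 points at 0.2 SD).

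The smallest observed difference that reaches significance is 1.984 × √(2/50) = 1.984 × 0.2 = 0.397 SD. With an assumed VAS SD of 2 points that is about 0.8 points on the 0–10 scale, and 0.6 to 1.0 points for an SD of 1.5 to 2.5.

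**The case against.** The best case for the plan is that H1 compares receiving the designed protocol with routine hospital care. Teaching, return demonstration and a booklet are how a self-applied package is delivered, and saying why to use it helps adherence. Both arms also hear the study aim, so controls are not naive. This stands as a reason not to call the teaching an error. It does not explain why one arm needs a statement of expected effects, or why training on a primary outcome scale should be described for one arm only.

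A reader might also draw stronger conclusions that the documents do not support:

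- **That study women get 60 to 80 minutes of benefit messaging.** The two sessions do add up to that time, but the benefit wording is part of one of four instruction items in the first. The paragraph that closes with the second session time covers compress technique and VAS training, with no benefit statement. That contact is one-to-one is itself an inference from the time being stated per woman.
- **That the 17% to 51% is the harm done by this wording.** It rests on an assumed total open-label expectation effect. Nothing in the documents sizes the part due to a few words.
- **That deleting those words removes the bias.** The woman knows her arm, and the Description of the protocol gives pain reduction as part of the pad's purpose. Much of the expectation would survive.
- **That controls are certainly untrained on the VAS.** The training sentence refers to each woman, so it may be meant for all. Its placement in the study-group section leaves this unclear, and both arms do complete a pain VAS at the initial assessment.
- **That the call order is fixed.** A list of items is not a mandated sequence.
- **That healing scores are affected in the same way.** The REEDA scale assesses wound condition and is not a self-rating. Its risk would be an assessor who knows the arm, which is a separate matter.

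**Conclusion.** The point holds as a modest, inexpensive improvement. With no blinding described and a self-rated primary outcome, the plan adds three avoidable differences: a benefit message to one arm, VAS training described for one arm, and a compliance item listed ahead of function at the study arm's 24-hour call. They can shift pain (6 h, 24 h, days 3, 5 and 7) and function (24 h, days 3 and 5) toward the study arm.

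The size is unknown. The 17% to 51% figure applies to one time point and rests on three assumptions: inert therapies, 50 analysed per arm, and a total expectation shift of 0.2 to 0.4 SD. It shows that a shift of that order would matter in a trial of this size; it does not show that such a shift will occur. The point does not invalidate the comparison of the package with routine care. It limits how far a pain difference can be credited to the physical therapies themselves.

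**What to change.** 1. Read the same short neutral instruction to both arms before every VAS, for example that it is not known which care gives better recovery and that she should rate only what she feels now. State that both arms receive the same VAS training.
2. At each call where function is rated, record pain and function before any compliance question. In practice this moves function ahead of pad compliance at 24 hours and fixes in writing the order already listed for days 3 and 5. At day 7, take the pain VAS first.
3. Keep the study-group script and booklet to neutral wording on what the pad is for and how to apply it, without promised effects.
4. Word the conclusion as the open-label effect of the protocol, including its teaching and contact time, versus routine care.

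The cost is editing one script, the booklet and the call sheet, plus a sentence read to each woman and the same brief VAS training for controls if they do not already get it. No visits, staff or participants are added. Less motivational wording might lower adherence slightly. The edits reduce the expectation bias but cannot remove it, which is why item 4 is needed alongside the others.

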Tool (E) Postpartum Follow up Sheet: This tool will be designed by the researcher after reviewing the related literature and will be revised by experts in gynecology and maternity nursing department and will include items to assess mother compliance with ice gel pad application through the first 24 hours and assess women's need for additional analgesia. Also, assess the women compliance with Kegel exercise performance from six hours postpartum till one week and compliance with the application of warm compresses per day from 48 hours postpartum till one week.

A designed Protocol of Care for Postpartum Perineal Trauma: It is a protocol developed by the investigator based on systematic reviewed studies done by (East; Begg; Henshall; Marchant; & Wallace (2009); Shahrahmani et al,(2016); East; Dorward; Whale;& Liu, (2020); Kridsana; Kunyanut; & Thitiporn (2020); and several studies as a quasi experimental time series study by Farrag, Eswi, & Badran,(2016); a randomized controlled trial by Derya, Ergul, Senol, & Aslan, (2017); and a quasi experimental study by Khosla & Pratibha, (2017); a quasi experimental study by Yuliani, Rizka,(2019).

The protocol entails a combination of evidence-based therapies for postpartum perineal trauma that is applied in steps starting from immediate postpartum and continues throughout the first week in order to relieve immediate and sustained perineal trauma.

Description of the protocol:

1. Application of perineal ice gel pad: Immediately postpartum (within 30 minutes to one hour) and through the first 24 hours postpartum to help reduce perineal pain, edema and stimulate repair process.
2. Postpartum performance of pelvic floor exercises (Kegel exercises): After six hours till one week postpartum to accelerate healing of perineal trauma and for further reduction of sustained perineal pain.
3. Postpartum perineal warm compresses: After 48 hours till one week postpartum to promote better healing of perineal trauma, prevent complications, prevent infection and further reduction of sustained perineal pain.

Ethical consideration

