For control group follow up by telephone call will be done at 24 hours to assess degree of perineal pain using Visual Analogue Scale for pain intensity (VAS), the women's need for additional analgesia and assess women's postpartum difficulty with functional activities as turning/ rolling in bed, getting out of bed, sitting, walking, defecation and urination using Visual Analogue Scale (VAS) for rating functional activities. Also, telephone follow up will be done at third and fifth day postpartum to assess degree of perineal pain using Visual Analogue Scale for pain intensity (VAS) and assess women's postpartum difficulty with performing functional activities as turning/ rolling in bed, getting out of bed, sitting, walking, defecation and urination using Visual Analogue Scale (VAS) for rating functional activities.

Then, a final postpartum follow up visit for both groups at the seventh day will be conducted for assessment of perineal trauma condition and healing process using

standardized REEDA scale and assess the degree of perineal pain using Visual Analogue Scale for pain intensity (VAS).

References

Davidson, N. (1974). REEDA: evaluating postpartum healing. *J Nurse Midwifery*. 1974; 9:6–9.

Derya, K., Ergul, Senol, &Aslan, E. (2017). The Effects of Cold Application to the Perineum on Pain Relief After Vaginal Birth, *Asian Nursing Research*, Volume 11, Issue 4, Pages 276-282, ISSN 1976-1317.

El-Saidy, T. M. K., Abou shady, R. M. N., &Soliman, H. F. A. (2018). Effect of Applying Crushed Ice Gel Pads on Episiotomy Pain and Wound Healing Among Postpartum Primiparous Women. *ijnd* 2018, 8, 19-29.

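### The 6-hour pain and REEDA scores are timed from ice-pad application in the study arm but from delivery in the control arm, a planned gap of up to about 1 hour

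*Combined protocol and SAP*

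**What the plan says.** All references are to the combined protocol and SAP.

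- **Intervention for the study group.** Pain (VAS) and wound condition (REEDA) are scored "six hours after the ice gel pad application, assessment of experienced perineal pain will be done using Visual Analogue Scale". The pad's own timing is "Immediately after delivery (within 30 minutes to one hour after delivery), an ice gel pad will be applied to perineal trauma". The Description of the protocol gives the same timing: "Immediately postpartum (within 30 minutes to one hour) and through the first 24 hours postpartum to help reduce perineal pain".
- **Same section, next paragraph.** Pelvic floor teaching is timed from birth, at six hours. It includes a vaginal examination by the investigator to check that the right muscles are used. The text does not say whether scoring comes before or after this.
- **Intervention for the control group.** The same two measures are taken "six hours after delivery, assessment of experienced perineal pain will be done using Visual Analogue Scale for pain intensity (VAS".
- **Other assessments.** At the start, "Initial assessment for women in both groups (study & control group) will be carried out". The first call is "For intervention group follow up by telephone call will be done at 24 hours to assess the following" in one arm and "For control group follow up by telephone call will be done at 24 hours to assess degree of perineal pain" in the other. The day 3 and day 5 calls have matching wording, and the last visit is "for both groups at the seventh day will be conducted for assessment of perineal trauma condition and healing process".
- **Outcome measures and Statistical plan.** Pain severity and delayed healing are the primary outcomes, with no time point named. Scores are compared between arms by an independent-samples t test, with no adjustment for time since delivery.

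**The concern.** A randomised comparison of scores needs both arms measured at the same time from an event they share. Here the event differs by arm at one assessment. Controls have no pad, so the study-arm clock cannot be applied to them, and the study-arm clock starts later than delivery. Because the offset is tied to the arm, randomisation does not remove it and a larger sample would not dilute it.

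If pain or REEDA is changing at around six hours, part of any difference between arms would reflect elapsed time and not the protocol of care. The pelvic floor session adds a second difference: followed literally, study women may be scored after an examination that controls are not described as having. Both primary outcomes are measured at this visit, and nothing in the plan excludes it from the primary analysis.

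**Working it through.** The plan states no figure for this gap, so there is none to reproduce. The check is arithmetic on the stated clocks.

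**Inputs**
- Delay *d* from delivery to first pad: 0.5 to 1.0 h (Description of the protocol; Intervention for the study group). Read as a ceiling only, *d* is more than 0 and at most 1.0 h.
- Study-arm scoring: 6 h after the pad.
- Control-arm scoring: 6 h after delivery.
- Pelvic floor session, study arm: due to start 6 h after birth.

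**Time since delivery at scoring**
- Study arm: *d* + 6 = 0.5 + 6 = 6.5 h, to 1.0 + 6 = 7.0 h.
- Control arm: 6.0 h.
- Gap: (*d* + 6) − 6 = *d*, which is 0.5 to 1.0 h, or up to 1.0 h on the ceiling reading.

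This takes the pad application to be the first one, which is the natural reading. The pad is re-applied every two hours, and counting from any later application would widen the gap.

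**Order relative to the pelvic floor session**
- Scoring is due at *d* + 6 h and the session at 6 h, so scoring falls due 30 to 60 minutes after the session is due to start.

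**How much of the schedule is affected**
- Post-baseline VAS: 6 h, 24 h, day 3, day 5, day 7. One of five is affected.
- Post-baseline REEDA: 6 h, day 7. One of two is affected.

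**From gap to bias**
- Bias in SD units = gap × change in score per hour. The documents give no hourly change for either scale and no sign.
- For illustration only, assume a drift of 0.02 to 0.2 SD per hour. The bias then runs from 0.5 × 0.02 = 0.01 SD to 1.0 × 0.2 = 0.2 SD. The range comes from the assumption and is not an estimate for this trial.

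**After the change**
- With both arms anchored at delivery, the planned gap is 6 − 6 = 0 h.

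**The case against.** The best defence is that this is loose drafting. The pad is described as going on at once after birth, so the authors may have treated pad application and delivery as nearly the same moment. Study women are also due for pelvic floor teaching six hours after birth, so the investigator should be with them at the control arm's time point anyway. Both points are fair, and they mean the gap is a feature of the written rule and not a demonstrated difference in conduct. They do not remove it: read literally, the study-arm text still holds two clocks, nothing reconciles them, and staff following it would score the arms at different times.

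A second defence is that controls need a different anchor because they have no pad. That is a reason to use the event both arms share, and the study-arm text already uses birth as a clock for the pelvic floor teaching.

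Three stronger readings are tempting, and the documents do not support them.
- *The 6-hour results are biased, or favour the study arm.* Nothing shows how fast, or in which direction, either score moves in that hour.
- *The assessments as a whole are misaligned.* The others are worded alike in both arms. Identical timing is not proved either: the initial assessment has no clock time and the 24-hour calls do not say what the 24 hours run from.
- *The primary comparison is compromised.* That depends on which time point is used. The missing primary time point is a separate matter; if day 7 were named, this mismatch would not touch the primary comparison.

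**Conclusion.** The point holds as a minor inconsistency in the assessment schedule. As written, study women have their 6-hour VAS and REEDA up to about 1 hour later after delivery than controls, and after the pelvic floor session is due to start. The planned gap is at least half an hour if the pad timing is a range of 30 to 60 minutes. Any 6-hour comparison therefore mixes treatment with time since delivery.

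This rests on two readings: that the clock starts at the first pad, and that staff follow the text literally. Confidence is high for the mismatch in wording and for the size of the gap. No claim is made about the size or sign of any effect on the scores. That it is probably modest is a judgement, based on a short gap at one assessment. Healing is less exposed than pain in one respect: the day 7 REEDA, which the plan itself ties to the healing process, is one visit described for both groups.

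**What to change.** 1. Reconcile the study-group and control-group text so that the 6-hour VAS and REEDA run from one event that both arms share, with the same stated window. Delivery is the natural choice, since controls have no pad.
2. State that scoring precedes the pelvic floor session, or otherwise fix the order. This is still needed with a delivery anchor, because scoring and the session would then fall due at the same hour.
3. Record each woman's actual assessment time on the follow-up sheet.
4. The Statistical plan is written in the past tense. If data are already collected, report actual assessment times by arm where they were recorded; if they were not, disclose the mismatch alongside any 6-hour result.

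The cost is wording changes and one time field, with no added visits or staff.
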